#### 1.4. Sample Size Justification

The calculation of the sample size is based on the primary efficacy endpoint (change from baseline to the end of Week 6 for the MADRS total score). The assumptions for the effect size were based on published literature and the clinically meaningful difference between groups to be detected.

The total sample size is calculated on the basis of the generalized Multiple Comparison Procedure-Modeling (MCP-Mod) test applied to the placebo and the JNJ-42847922 dose groups at the final analysis. Approximately 280 randomized subjects will provide an average weighted power of approximately 85% depending on the underlying true dose-response shape, assuming a 1-sided significance level of 0.05, a treatment difference from placebo of 4.5 points in change in MADRS total score, a standard deviation of 10, and a 25% overall dropout rate.

The data cutoff for the interim analysis will be 6 weeks after randomization of 160 subjects, which corresponds to approximately 57% of the sample size of the study. This number of subjects provides approximately 93% power to detect a dose-response relationship, depending on

the underlying true dose-response shape, assuming a treatment difference of 4.5, and a standard deviation of 10 when tested by means of the MCP-Mod approach at the 30% significance level (1-sided).

Further details regarding the interim analysis will be specified in a separate charter and interim analysis SAP.

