## 5.1. Analysis Specifications

## 5.1.1. Level of Significance

The primary efficacy endpoint will be evaluated at a 1-sided significance level of 0.05 using the MCP-Mod approach to test for dose-response. For all other analyses of the primary efficacy

endpoint and for all other efficacy endpoints, no multiplicity adjustment will be done will be presented.

For the interim analysis, a 1-sided 0.30 significance level will be used to test for dose-response using the MCP-Mod approach on the change in MADRS total score to the end of Week 6. No adjustment to the final significance level will be performed due to the interim analysis.

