## 5.2.3.1. MCP-Mod Analysis

The primary efficacy endpoint will be evaluated using the generalized MCP-Mod approach. The MCP-Mod approach provides a method for dose-finding using model-based estimation rather than hypothesis testing via pairwise comparisons. The analysis will be done in two steps.

First, a mixed model for repeated measures (MMRM) analysis of the observed data from the placebo and JNJ-42847922 groups will be used as the method of addressing missing data and to

adjust for important covariates. The MMRM will include region (as defined in Section 2.6), time (scheduled Week), treatment (placebo and JNJ-42847922 dose groups), baseline insomnia status (present/absent), and treatment-by-time interaction as factors and baseline MADRS total score as a covariate. An unstructured variance-covariance matrix will be used for observations clustered by subject. In case of convergence problems, alternative variance-covariance structures will be tried in the following order, with the first structure that converges being used in the analysis: heterogeneous Toeplitz, standard Toeplitz, and AR(1) with separate subject random effect. Subjects in the full analysis set who do not have complete data will still contribute to the estimates at the end of Week 6, but will have less weight in the analysis than those subjects with complete data. The Kenward-Roger method will be used for approximating the denominator degrees of freedom. Based on the MMRM, the least-squares (LS) mean estimates for each JNJ-42847922 dose group and placebo at Week 6 and the corresponding variances will be obtained.

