## 5.2.3.4. Mediation Analysis

In the mediation analysis framework, natural direct effect can be conceived of as the independent treatment effect on the outcome (i.e., change in MADRS total score) that is above and beyond its effect on the mediator (i.e., change in ISI score); controlled direct effect can be conceived of as the independent treatment effect on the outcome controlling the mediator at a fixed level; and natural indirect effect can be conceived of as a treatment effect on the outcome that is accounted for by its effect on the mediator.

A mediation analysis will be performed to examine the mediating role of improvement in sleep assessed by change from baseline in ISI score on change from baseline in MADRS total score provided that both endpoints demonstrate a statistically difference between at least one dose of JNJ-42847922 and placebo. This analysis will assess the extent to which change in MADRS total score may be mediated by or independent of change in ISI score based on observed data (i.e., data collected at each time point without carrying forward previous values) at the end of Week 6. The analysis will consider both change in MADRS total score and change in ISI score as continuous variables. The calculation of the ISI score is described in Section 5.2.3.5.

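### The mediation analysis has no missing-data method: if dropout depends on earlier MADRS scores and differs by arm, the direct effect and the sleep-mediated share can be biased in either direction

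*SAP*

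**What the plan says.** SAP 5.2.3.4 asks how much of the MADRS effect passes through improvement in sleep, measured by change in ISI. It then asks the same question in reverse. Both runs are "based on observed data (i.e., data collected at each time point without carrying forward previous values) at the end of Week 6". The section gives no imputation, weighting or missing-data sensitivity analysis. The LOCF analyses listed in SAP 5.1.2 cover MADRS, MADRS-6, HAM-A and PHQ-9, not mediation. The analysis is gated: it runs "provided that both endpoints demonstrate a statistically difference between at least one dose" of study drug and placebo.

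The primary analysis treats the same gaps differently. SAP 5.2.3.1 specifies an MMRM that "will be used as the method of addressing missing data", and subjects with incomplete data still contribute. The primary estimand in SAP 5.2.2 is the effect had everyone stayed on treatment. SAP 1.4 plans for "a standard deviation of 10, and a 25% overall dropout rate".

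Two further rules bear on who enters the models. In SAP Table 1 the MADRS Day 42 window opens at Day 33, whereas the ISI Day 42 window opens at Day 2. Protocol 10.2 calls for end-of-treatment assessments when a subject withdraws early, and the Time and Events Schedule places an ISI at that visit.

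**The concern.** A subject who leaves before Day 33 has no Day 42 MADRS and drops out of the outcome model, even though any Day 8 and Day 22 MADRS and PROMIS-SD scores are in the database. If those who leave are selected on earlier response, and selected differently by arm, the remaining subjects no longer give an unbiased treatment contrast. The direct effect absorbs most of the distortion.

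The documents make arm-specific dropout plausible without showing that it will occur. Under Protocol 10.2, stopping treatment means withdrawal from the study. The listed reasons include tolerability and acute suicidal ideation with a clear plan. In the earlier multiple-dose MDD study (Protocol 1.1.2), among men and women of non-childbearing potential, somnolence occurred in 3 of 12 subjects on drug, 0 of 6 on placebo and 0 of 7 on diphenhydramine.

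At stake is the one analysis in the SAP that divides the MADRS effect into sleep-mediated and independent parts. There is also a gap in definition. An early leaver can have a Day 42 ISI and no Day 42 MADRS, and the SAP does not say whether the mediator and outcome models use the same subjects.

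**Working it through.** **1. The plan's own figure.** SAP 1.4 states: "Approximately 280 randomized subjects will provide an average weighted power of approximately 85" per cent, for "a treatment difference from placebo of 4.5 points", SD 10, 1-sided 0.05 and 25% dropout. Evaluable subjects: 280 × 0.75 = 210, or 105/52.5/52.5 at 2:1:1. With the SAP's three candidate models and optimal contrasts, power is 84.1% (linear), 92.6% (emax) and 81.8% (exponential). The mean is 258.5/3 = 86.2%. Adding 10 mg, with the last 120 subjects allocated 2:1:1:1 (my assumption), gives 85.2%. Check for one dose against placebo: 4.5/(10√(1/105 + 1/52.5)) = 2.66; 2.66 − 1.645 = 1.02; power 84.6%. The planning inputs hold together.

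**2. Subjects at risk of exclusion.** 280 × 0.25 = 70. Subjects who leave from Day 33 onward with an end-of-treatment MADRS still count as Day 42, so 70 is a planning figure and not a prediction.

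**3. Simulation model.** From the SAP: total effect -4.5, SD 10, 25% dropout. Assumed, because the documents give no values:
- ISI change M = aT + error, with SD 6.
- MADRS change Y = c′T + bM + error, with b = 0.7.
- Direct effect c′ = -2.7 and indirect effect ab = -1.8, so a = -1.8/0.7 = -2.57 and the true share is 1.8/4.5 = 40%.
- Day 22 to Week 6 residual correlation about 0.6.
- Log-odds of dropout rise by k per SD of Day 22 MADRS.

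Completers were analysed with Y on T, M and T×M, and M on T. Share = indirect/(direct + indirect). Each scenario had 1.5 million subjects, so simulation error is small.

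| Dropout | Direct | Indirect | Sum | Share |
|---|---|---|---|---|
| Unrelated to outcome, 25%/25% | -2.68 | -1.81 | -4.49 | 40% |
| Unrelated to outcome, 20%/30% | -2.70 | -1.82 | -4.52 | 40% |
| Same rule in both arms, k = 0.5 / 1 / 2 | -2.65 / -2.54 / -2.38 | -1.76 / -1.71 / -1.57 | -4.42 / -4.25 / -3.95 | 40% each |
| Placebo only, k = 0.5 / 1 / 2 | -2.12 / -1.67 / -1.14 | -1.68 / -1.58 / -1.46 | -3.80 / -3.25 / -2.60 | 44% / 49% / 56% |
| Drug only, k = 1 / 2 | -3.80 / -4.46 | -1.94 / -1.97 | -5.74 / -6.43 | 34% / 31% |

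An estimate that keeps dropouts through their Day 22 MADRS returned a total of -4.47 to -4.54 in every scenario.

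**4. Dependence on the assumed share.** With a true share of 20%, placebo-only dropout gives 21% to 22% and drug-only gives 19% to 18%. With 60%, the figures are 68% to 92% and 49% to 44%. A second parameter set (direct -3.0, indirect -1.5, share 33%, b = 0.5, correlation 0.7) gives 39% and 44% for placebo-only dropout at k = 0.5 and 1, and 29% and 27% for drug-only. The same mechanism and rate in both arms gives -3.1 and -1.4, a share of 1.4/4.5 = 31%.

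**5. Against sampling noise.** For 105 placebo and 52 single-dose completers with b = 0.5, the residual SD is √(100 − 0.5² × 6²) = 9.5. The direct-effect standard error is then at least 9.5√(1/105 + 1/52) = 1.6; simulation gives about 1.7. The middle 90% of the estimated share runs from about 12% to 82%, and is wider once the SAP's treatment-by-ISI-change interaction is fitted.

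**The case against.** The analysis is openly labelled observed-case, is gated on both endpoints, carries no alpha and does not touch the primary test: "The primary efficacy endpoint will be evaluated at a 1-sided significance level of 0.05" by MCP-Mod. It is not the only evidence on sleep. MADRS-6 (SAP 5.3.15) omits the reduced-sleep item, and SAP 5.2.3.5 examines baseline ISI. Most of the simulated shifts are small against the sampling spread in step 5. All of this stands and limits the weight of the point, although a systematic shift is not removed by being smaller than the noise.

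The evidence that imputation recovers the truth is partly built in, because dropout was simulated to depend on Day 22 MADRS and the estimator used Day 22 MADRS. That also stands. It shows that the remedy works if MAR holds, not that MAR holds.

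A reader might infer three stronger things that the documents do not support:
- **That 25% dropout by itself biases the direct effect.** Dropout unrelated to outcome gave no bias, even at 20%/30%.
- **That the sleep-mediated share will be overstated.** That is the placebo-only case. Score-related dropout on drug only reverses it, and the SAP gives a single overall rate with no split by arm or reason.
- **That a gap between direct plus indirect and the MMRM effect is a contradiction.** The SAP never says that the two should agree. It is a limit on interpretation.

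**Conclusion.** The point holds in conditional form. Both mediation runs lack a missing-data method while the primary model uses partial data under MAR. If dropout depends on earlier MADRS scores and that dependence differs by arm, the direct effect and the share can be wrong in either direction. From a true share of 40%, the range is 31% to 56%, and direct plus indirect runs from -2.6 to -6.4 against -4.5. With dropout unrelated to outcome, or following one rule in both arms, the share barely moves, though one common rule can attenuate the sum (to -3.95 at k = 2).

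These sizes rest on assumed values for the ISI effect, the ISI-to-MADRS slope, the visit correlation and the dropout rule. The documents supply none of them, so neither sign nor size can be settled in advance. That is a reason to pre-specify a second version. The mismatch between the ISI and MADRS Day 42 windows stands on the text alone. I grade this as a cheap improvement to a gated, supportive analysis.

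**What to change.** In SAP 5.2.3.4:

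- Define one common analysis set for the mediator and outcome models, in both directions.
- For this analysis, count an ISI as Week 6 only if it falls in the MADRS Day 42 window (Day 33 to end of double-blind). Otherwise an early-withdrawal ISI would stand as a Week 6 value and never be imputed.
- Add a pre-specified multiple-imputation version under MAR, by treatment arm, for both mediation runs. Use baseline values, Day 8 and Day 22 MADRS and PROMIS-SD, any early-withdrawal ISI, region and insomnia status. Fit the mediation models in each imputed data set, combine them, and state how.
- Report it beside the observed-case version.

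The cost is SAP wording and some programming; no new data are needed. The imputed version relies on the MAR assumption that the primary MMRM already makes. The ISI imputation leans on MADRS and PROMIS-SD, because ISI has only one scheduled post-baseline assessment.

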3.2. Study Design Rationale

Study Population

In the context of mood disorders, sleep disturbances (both insomnia and hypersomnia) have been associated with a suboptimal response to antidepressant drug therapy, an increased risk for relapse (in antidepressant-responsive patients), and prodromal depression. 4,5,24,25,59 While the

orexin system promotes wakefulness, increasingly it is also associated with hyperarousal³ and motivational behaviors. Hyperarousal characterizes a major subgroup of patients with MDD. NX2R antagonists may have utility to normalize hyperarousal in patients with MDD and thereby have an antidepressant effect independent from their utility as hypnotics. It is proposed that in many patients a cycle exists that involves rumination/dysphoric arousal leading to sleep problems, thereby perpetuating/exacerbating a depressive episode. Therefore, OX2R antagonists, such as JNJ-42847922 may have clinical efficacy in the treatment of MDD, particularly in patients with such symptoms, and especially as an adjunctive therapy to conventional antidepressant drug therapy.

The study population will include adult men and WONCBP (aged 18 to 70 years, inclusive) who meet DSM-5 diagnostic criteria for MDD (confirmed by the SCID-CT), ¹⁵ and who have had an inadequate response to current antidepressant therapy with an SSRI/SNRI (administered at an adequate dose and duration in the current episode). The diagnosis of MDD will be validated by the SSQ. The SSQ criteria identify subjects who, despite meeting DSM criteria, would be poor candidates for drug trials and whose exclusion from the study may increase the likelihood of separation between novel antidepressant treatments and placebo.

Unlike many other mental disorders, the age of onset of depression has a wide range, with a median onset of early to mid-20s, although significant proportions of patients may experience onset between late adolescence to late adulthood. Hence, the age of the study population in this protocol is intentionally broad. Women have a two-fold increased risk of depression over men, and separation and divorce are additional risk factors across the sexes.²⁶

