#### 1.5. Randomization and Blinding

Central randomization will be implemented in this study. Subjects will be randomly assigned based on a computer-generated randomization schedule prepared before the study by or under the supervision of the sponsor.

At the start of study enrollment, subjects will be randomly assigned to receive 1 of 3 treatments in a 2:1:1 ratio to placebo:JNJ-42847922 20 mg:JNJ-42847922 40 mg.

After the interim analysis, subjects will be randomly assigned to study drug, with the allocation ratio adapted according to the dose-response curve observed at the time of the interim analysis. Subjects will be assigned to receive placebo or one of the JNJ-42847922 doses (potential doses include 10 mg, 20 mg, 40 mg).

The randomization will be balanced by using randomly permuted blocks and will be stratified by region (United States [US], Europe, and Japan) and by insomnia status (significant insomnia symptoms [ISI score  $\geq$ 15] at baseline versus no significant insomnia symptoms [ISI score <15] at baseline). In order to randomize approximately equal proportions of subjects with and without significant insomnia symptoms at baseline, the number randomized in either stratum will be capped at 60% of the planned total sample size.

The interactive web response system (IWRS) will assign a unique treatment code, which will dictate the treatment assignment and matching study drug kit for the subject. The requestor must use his or her own user identification and personal identification number when contacting the IWRS, and will then give the relevant subject details to uniquely identify the subject.

To maintain the study blind, the study drug container will have a label containing the study name, study drug number, and reference number. The label will not identify the study drug in the container. However, if it is necessary for a subject's safety, the study blind may be broken and the identity of the study drug ascertained. The study drugs will be identical in appearance and will be packaged in identical containers.

In general, randomization codes will be disclosed fully only when the study is completed and the clinical database is closed. However, for the interim analysis, the randomization codes and the translation of randomization codes into treatment and control groups will be disclosed to those authorized and only for those subjects included in the interim analysis.

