• Simulation-based Counterfactual Approach: this analysis introduced by Imai et.al  obtains the natural direct effect and natural indirect effect using numerical simulations. The approach uses parametric bootstrapping to construct the point estimate and its uncertainty estimates for direct effect and indirect effect from the bootstrap sampling distribution. For each bootstrapped sample, change from baseline in MADRS total score and change from baseline in ISI score will be analyzed. The ANCOVA analysis of change in MADRS total score from baseline will include factors for treatment (placebo and JNJ-42847922 dose groups), region, and baseline insomnia status (present/absent), change from baseline (Day 1, predose) in ISI score, treatment-by-change from baseline in ISI score as a covariate. The ANCOVA analysis of change in ISI score will include factors for treatment (placebo and JNJ-42847922 dose groups), region, and baseline MADRS total score as a covariate. The ANCOVA analysis of change in ISI score will include factors for treatment (placebo and JNJ-42847922 dose groups), region, and baseline MADRS total score as a covariate. The ANCOVA analysis of change in ISI score will include factors for treatment (placebo and JNJ-42847922 dose groups), region, and baseline insomnia status (present/absent), and baseline MADRS total score as a covariate. Estimate of the controlled direct effect will be obtained by plugging in the estimated coefficient values and the mean level of change in ISI score into the analytic expressions.

Since the relationship can be bi-directional, a mediation analysis similar to the above analysis will be performed, to assess the extent to which change in ISI score may be mediated by or independent of change in MADRS total score, based on observed data (i.e., data collected at each time point without carrying forward previous values) at the end of Week 6.

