## 5.3.3.2. Analysis Methods

The shift in ISI score category from baseline to the end of Week 6 will be presented. A frequency distribution of the ISI individual item scores at each time point will be provided by treatment group. In addition, descriptive statistics of the ISI score at Baseline and Week 6, as well as the change from baseline to Week 6, will be presented by treatment group. Descriptive statistics will also be provided for change from baseline to the end of Week 6 in ISI total score by baseline ISI score ( $\geq$ 15 versus <15, using the randomization stratification factor as entered into IWRS)

The change in ISI score from baseline to the end of Week 6 will be analyzed using an ANCOVA model. The ANCOVA model will include factors for treatment and region, and baseline ISI score as a continuous covariate. A 90% CI for the difference in LSMeans and p-value will be calculated based on the contrast test statistic for each JNJ-42847922 dose level.

The cumulative response rate, defined as the percentage of subjects experiencing at least a given value of percent reduction from baseline to the end of Week 6 in ISI score, will be presented graphically, using observed data.

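### The mediation models adjust for the binary insomnia stratum but not for continuous baseline ISI, so the sleep-mediated share of the MADRS effect is exposed to residual confounding of unknown size and sign

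*SAP*

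**What the plan says.** SAP 5.2.3.4 plans a simulation-based mediation analysis with change in ISI as mediator and change in MADRS total score as outcome, on observed Week 6 data. It runs only if both endpoints separate from placebo for at least one dose. A reversed analysis, with the two changes exchanging roles, is described only as similar.

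The fullest readable covariate list for the ISI-change model is treatment, "region, and baseline insomnia status (present/absent), and baseline MADRS total score as a covariate". The MADRS-change model lists treatment, region, insomnia status, ISI change and its interaction with treatment. The baseline ISI score appears in neither.

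SAP 2.8 defines baseline insomnia status for the analyses as the stratification factor entered in IWRS, ISI 15 or more versus below 15. The score itself is collected on Day 1 (Protocol, Time and Events Schedule).

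For the same ISI-change variable, SAP 5.3.3.2 says: "The ANCOVA model will include factors for treatment and region, and baseline ISI score as a continuous covariate". SAP 5.2.3.5 also examines baseline ISI as a continuous correlate of MADRS change. Protocol 3.2 notes that "sleep disturbances (both insomnia and hypersomnia) have been associated with a suboptimal response to antidepressant drug therapy".

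**The concern.** Natural direct and indirect effects require that nothing left out of the models drives both mediator and outcome. Randomisation secures the treatment comparison but not the link between ISI change and MADRS change. ISI change depends on where ISI started. If baseline ISI also bears on MADRS change once ISI change is held fixed, it confounds that link, and a two-level stratum removes only part of the problem.

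At stake is how much of any antidepressant effect is credited to better sleep. Protocol 3.2 proposes an antidepressant effect separate from the hypnotic one, and 5.2.3.4 is the SAP's formal look at that question. The covariate is in hand, and the SAP gives no reason for departing from 5.3.3.2.

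**Working it through.** **Plan's own figure.** No power, precision or effect figure is stated for the mediation analysis. The nearest is the primary sample size, used here only to set the scale: "Approximately 280 randomized subjects will provide an average weighted power of approximately 85" per cent, for "a treatment difference from placebo of 4.5 points in change in MADRS total score", with "a standard deviation of 10, and a 25% overall dropout rate". Evaluable: 280 × 0.75 = 210. With the initial allocation "in a 2:1:1 ratio to placebo:JNJ-42847922 20 mg:JNJ-42847922 40 mg" (105/52.5/52.5 evaluable), the SAP's three candidate shapes and the rule "The primary efficacy endpoint will be evaluated at a 1-sided significance level of 0.05 using the MCP-Mod approach to test for dose-response", power is 84.3% (linear), 92.7% (emax) and 82.0% (exponential), mean 86.3%. That agrees with the plan and is not in dispute.

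**What the stratum leaves.** For a normal score cut at z, the share of variance captured is φ(z)² / [p(1−p)]. Assume mean 14.5 and SD 6 (Protocol 3.2 cites means of about 14 to 15; the SD is assumed). Then z = 0.5/6 = 0.083, φ = 0.398, p = 0.467, giving 0.158/0.249 = 0.635. Within-stratum variance is 36 × 0.365 = 13.1.

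**Bias formula.** Write ISI change as M = aT − λB + e and MADRS change as Y = c′T + bM + gB + u, where B is baseline ISI and there is no treatment-by-mediator interaction. Omitting B within stratum gives

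bias in b = −g · λV / (λ²V + s²),

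with V the within-stratum variance of B and s the SD of e. The mediated effect is a·b. The bias vanishes when g = 0. Since M is Week 6 ISI minus B, Y contains b·(Week 6 ISI) + (g − b)·B. So g = 0 means that the two ISI scores carry equal and opposite weights, and g = b means that only the Week 6 level matters.

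**Assumed inputs (none in the documents).** a = −3, b = 0.5, so the true mediated effect is −1.5 and the share 1.5/4.5 = 33.3%; two equal groups, 210 evaluable; λ = 0.4; V = 13.1. The simulated SE of a with continuous ISI, 0.62, implies s = 0.62/√(4/210) = 4.5. Then λV/(λ²V + s²) = 5.24/(2.10 + 20.25) = 0.235.

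| g | b with stratum only | share by formula | simulated share, stratum | simulated share, continuous | SE of mediated effect, stratum / continuous | root MSE, stratum / continuous |
|---|---|---|---|---|---|---|
| −0.5 | 0.617 | 41% | 41% | 33% | 0.544 / 0.497 | 0.640 / 0.497 |
| −0.25 | 0.559 | 37% | 37% | 33% | 0.517 / 0.494 | 0.543 / 0.494 |
| 0 | 0.500 | 33% | 33% | 33% | 0.494 / 0.495 | 0.494 / 0.495 |
| +0.25 | 0.441 | 29% | 30% | 33% | 0.463 / 0.488 | 0.491 / 0.488 |
| +0.5 | 0.383 | 26% | 26% | 33% | 0.456 / 0.494 | 0.563 / 0.494 |

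**Range.** Over λ of 0.2 to 0.6 and baseline SD of 4 to 6, the lowest simulated share is 23% (λ = 0.6, SD 6, g = +0.5). The highest is 41% (g = −0.5, run at λ = 0.4 only). The corner λ = 0.6, g = −0.5 was not simulated. By the formula, b = 0.5 + 0.5 × 7.86/(4.72 + 20.25) = 0.657, a share of 3 × 0.657/4.5 = 44%.

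**Precision.** Stratum only versus continuous, the SE of the treatment effect on ISI change is 0% to 11% larger. The SE ratio for the mediated effect is 0.86 to 1.11. Adding baseline ISI can therefore cut that SE by about 10% (1/1.11 = 0.90) or raise it by up to 16% (1/0.86 = 1.16), and by 8% in the last table row (0.494/0.456).

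**The case against.** Much can be said on the other side.

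- **The key input is missing.** Bias needs g to differ from zero, and nothing in the documents gives g. The remark in Protocol 3.2 is unquantified, covers hypersomnia as well as insomnia, and is not conditional on ISI change. A reader might infer that the split is biased, and biased towards a sleep-independent effect. The documents support neither: the bias may be zero or go either way. This stands.
- **No general gain in precision.** A reader might expect the extra covariate to sharpen the mediated share. It sharpens the treatment effect on ISI change, but usually widens the SE of the mediator slope. In one assumed setting (52 on one dose versus 105 on placebo, ISI effect −2, MADRS residual SD 8, g = +0.5) the SE of the mediated effect rises from 0.47 to 0.56. Root mean squared error is about 0.53 without the covariate and 0.56 with it. This stands too; the fix is not free.
- **Bias is modest against noise.** At g = +0.5 in the table it is 1.500 − 1.176 = 0.324 MADRS points, about 0.7 of the SE of 0.456; at +0.25 it is 0.164, about 0.35 of 0.463. Fair, though noise is reported in an interval and this bias is not.
- **Consequence is limited.** The analysis is conditional, is not a protocol endpoint and is not in SAP Table 4. Sleep is also addressed by ISI subgroups, the baseline ISI correlation and MADRS-6, which omits the sleep item. This lowers priority.
- **The text is uncertain.** The available copy of 5.2.3.4 repeats the ISI-change sentence with differing lists and garbles the MADRS-change sentence, probably through PDF extraction. That is no fault of the plan, but the lists should be checked against the source. No readable version contains baseline ISI.

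**Conclusion.** The point holds as an exposure, not as a demonstrated bias. As readable, both mediation models carry at most the ISI 15 stratum. About 37% of baseline ISI variance is then unadjusted if ISI is roughly normal and cut near its mean, whereas the SAP adjusts for the full score when it analyses ISI change on its own. Under the assumed inputs, a true 33% mediated share is reported as about 23% to 41%. It is reported correctly when baseline ISI has no effect on MADRS change given ISI change, and in every simulated scenario once continuous baseline ISI is in both models. No general precision gain is claimed.

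The primary MCP-Mod test, the pairwise contrasts and the total treatment effect on MADRS do not depend on this choice. Confidence is moderate because of the state of the text: if the source SAP lists baseline ISI in both models, the point falls away. Cheap improvement, low to moderate priority.

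**What to change.** In SAP 5.2.3.4, add the baseline ISI total score as a continuous covariate to both the ISI-change and the MADRS-change models. Do the same in the reversed analysis, and write out its models instead of calling them similar. Keep region and the insomnia stratum. Restate each model's covariate list once and cleanly, including whether baseline MADRS is in the MADRS-change model.

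Cost: one covariate in wording and code, and a standard error for the mediated effect that may move by roughly 10% either way, or somewhat more upwards in unfavourable settings. No new data are needed. Reporting the stratum-only fit alongside would show how far the split depends on the choice.
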